6.0 Analysis Conventions

This section provides general considerations for data handling, summary, and analysis. This also includes general definitions of certain kinds of endpoints. More details about specific endpoints and additional analysis methods, as needed, will be specified within the description of analysis of data in this SAP.

Continuous variables will be summarized by sample size (N), mean, standard deviation (St. Dev.), median, minimum, and maximum. Frequency and percentage will be provided for categorical variables and 95% confidence intervals (CIs) will be generated for parameter estimates of interest.

Dealing with Multiple Values on the Same Day for Lab and Vital Signs Parameters

In cases where multiple values for the same variable are collected on the same day (including baseline visit and post-baseline visits), the arithmetic average will be calculated and used as the value for that day for mean changes in laboratory and vital signs parameters.

Definition of Baseline Observation

Unless otherwise specified, the baseline observation is defined as the last non-missing measurement collected prior to or on randomization. If no measurement collected prior to or on randomization, then the last non-missing observation prior to or on the first dose date of study drug (ABT-414/TMZ/lomustine) is considered.

Definition of Final Observation

For lab and vital sign parameters, the final observation is defined as the last non-missing post-baseline measurement collected during the study.

Definition of Study Rx Days (Days Relative to the First Dose of Study Drug)

Study Rx Days are calculated for each time point relative to the first dose date of study drug (ABT-414/TMZ/lomustine). They are defined as the number of days between the day of the first dose of study drug (ABT-414/TMZ/lomustine) and the specific time point. Rx days are negative values when the time point of interest is prior to the first study drug dose day. Rx days are positive values when the time point of interest is after the first study drug dose day. The day of the first dose of study drug (ABT-414/TMZ/lomustine) is defined as Study Rx Day 1, while the day prior to the first study drug dose is defined as Study Rx Day -1 (there is no Study Rx Day 0).

Definition of Analysis Windows

During the treatment period, all time points and corresponding time windows are based on Study Rx Days, unless specified otherwise. For longitudinal analyses, especially for the laboratory data, the time windows in Table 2 describe how data collected at protocol specified visits will be assigned. If more than one observation is included in a time window, the observation closest to the nominal day should be used. If there are two observations equally distant to the nominal day, the later one will be used in analyses.

Table 2. Visit Window

Study Visit (Week)*	Nominal Study Rx Day	Time Window (Study Rx Days Range)
Baseline	-	By baseline definition
2	15	2 to ≤ 18
3	22	19 to ≤ 25
4	29	26 to ≤ 32
...
X	$7 \cdot X + 1$	$7 \cdot X - 2$ to $\leq 7 \cdot X + 4$

* ECG at baseline and only Day 1 of Cycle 1 and 3, immediately after ABT-414 infusion and only subjects treated with ABT-414 (Arms 1 or 2).

Time-to-Event Endpoints

All time to event (TTE) endpoints are defined using a time variable and an event indicator. The time variable represents the time from a pre-defined time origin to the onset of a predefined event of interest or the last time when adequate assessments have been made to rule out the onset of the event. The latter case indicates that the endpoint has been right-censored. The event indicator is set to 1 if the event has been observed during the course of the study and 0 if it is censored. When multiple assessments are needed to ascertain the occurrence of an event, the earliest date among all of these assessments is taken to be date of the event or censoring. The time variable will be computed in days and converted into months (1 month = 30.4375 days) for analysis of TTE endpoints. When no post-randomization observations are available for a subject for any given endpoint, then the endpoint is taken to be censored on the date of randomization.

All TTE endpoints defined in this study are concerned with only the first incidence of an event of interest, and recurrence of the same event is not considered. An event, however, may be defined in a composite fashion, i.e., as the occurrence of one among several different outcomes. An example of such an endpoint is PFS where the event is either disease progression or death. The composite event is observed when at least one of the component events occurs, and the time to the earliest among the occurring component events is considered to be the TTE for the composite event.

Prior and Concomitant Medications

A prior medication is defined as any medication with an end date prior to the date of randomization and collected on the electronic case report forms (eCRFs). A concomitant medication is defined as any drug that started on the day of or after randomization, but not 35 days after the last protocol drug administration. Medications with a start date prior to the date of randomization and continuing after randomization are also classified as concomitant medications. A medication will also be considered a concomitant medication if one of the following three cases occur: (1) the start date is missing and the end date is

either after or on the day of randomization; (2) the start date is not missing but not 35 days after the last protocol drug administration and the end date is missing; (3) both the start date and the end date are missing.

End of Study

End of study occurs when all of the following criteria have been satisfied:

- At least 118 deaths have been observed for each treatment arm comparison versus control,
- Thirty five days have passed since all subjects have stopped protocol treatment, and
- The database has been fully cleaned and frozen for analyses.

7.0 Demographics, Baseline Characteristics, Medical History, Previous/Concomitant Medications, and Prior Oncology Therapies

Data for demographic, baseline characteristics, medical history, previous/concomitant medications, and prior oncology therapies will be summarized for each treatment arm and overall on the ITT population.

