Arm 2: patients will be treated with ABT-414 monotherapy 1.0 mg/kg IV infusion over 30 to 40 minutes once every 2 weeks until one of the treatment withdrawal criteria has been met.

Arm 3: Patients in the control arm will be treated according to the timing of relapse.

Arm 3A: Patients relapsing during TMZ treatment or within the first 16 weeks after the first day of the last TMZ cycle will be treated with lomustine 110 mg/m² on day 1 of every 42-day treatment period.

Treatment will continue until one of the treatment withdrawal criteria has been met. Lomustine will be given for a maximum of one year.

Arm 3B: Patients relapsing 16 weeks or more after the first day of the last TMZ cycle will be treated with TMZ 150 mg/m² on day 1 to 5 for the first 28-day cycle, with dose escalation to 200 mg/m² in subsequent cycles in case of adequate tolerance. Treatment will continue until one of the treatment withdrawal criteria has been met.

[figure not shown]
Treatment should start within 96 hours from randomization.

Treatment at further progression will be according to investigators discretion. Day 1 of the first cycle will be the first day when the study medication is taken.

There will be an interim futility analysis organized. At interim analysis one or both of the ABT-414 arms might be discontinued based on lack of efficacy for PFS (Reject H1 in favor of H0) according to RANO criteria assessed by IRC (see section 8.3).

Disease will be assessed by study-specific MRI according to the study specific imaging protocol every 8 weeks. Response and progression will be assessed by the RANO criteria (see section 7.1).

The safety profile will be assessed separately for each cycle of therapy with CTCAE v4 (see section 7.2).

5 Therapeutic regimens, expected toxicity, dose modifications

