11.4 Analysis of Laboratory, Vital Signs, and ECG Data

Biochemical parameters (serum creatinine, total bilirubin, AST, ALT, alkaline phosphatase, phosphate, total protein, albumin, sodium, potassium, calcium, and chloride) will be collected at baseline (all Arms), and Day 1 of each cycle (all Arms).

Hematological parameters (WBC, absolute neutrophil count, lymphocytes, hematocrit, hemoglobin, and platelet count) will be collected at baseline (all Arms), Day 1 of each cycle (all Arms), Day 14 of each cycle (Arms 1 and 2 only), Day 21 of each cycle (Arms 1 and 3B only), and Day 28 of each cycle (Arm 3A only).

Vital sign parameters (diastolic/systolic blood pressure, pulse rate, and body temperature (°C)) will be collected at baseline (all Arms), Day 1 of each cycle (all Arms), Day 14 of each cycle (Arms 1 and 2 only), and Day 28 of each cycle (Arm 3A only), and follow-up visit if clinically indicated/relevant.

Twelve-lead ECG data will be collected at baseline, immediately after ABT-414 dosing on Day 1 of Cycle 1 and Cycle 3 (Arms 1 or 2 only).

For hematological, biochemical, and vital sign parameters, changes from baseline are analyzed for each post-baseline visit (as specified in Section 6.0 Analysis of Conventions) and the final visit. If more than one measurement exists for a subject on a particular day, an arithmetic average will be calculated. The average will be considered to be the subject's measurement of that day. Descriptive statistics will be presented for baseline, each post-baseline, and the final visit by each treatment arm. Mean change from baseline to each post-baseline visit and the final visit within each treatment arm will also be presented. The highest and lowest values of each hematological parameter will be identified for each subject, and descriptive statistics for mean change from baseline within each treatment arm will be presented.

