Biochemistry and hematology determinations will be categorized according to NCI CTCAE version 4.0 grades, and shifts from baseline grades to maximum and final post-baseline grades will be assessed. The baseline and final grades will be defined respectively as the grade of the last measurement collected prior to or on randomization, or if missing, then prior to or on the first dose of study drug (ABT-414/TMZ/lomustine), and as the grade of the last post-baseline measurement collected no more than 35 days after the last dose of study drug (ABT-414/TMZ/lomustine). If multiple values are available for a post-baseline measurement, then the value with the highest NCI CTCAE

grade will be used in the assessment of shift. Frequency and percentage of subjects will be presented by treatment arm: 1) baseline grade vs. maximum post-baseline grades, and 2) baseline grade vs. final post-baseline grade. Frequency and percentage of subjects experiencing a shift from baseline grades of 0 to 2 to maximum post-baseline grades of 3 to 4, and from baseline grades of 0 to 2 to final post-baseline grades of 3 to 4 will be presented by treatment arm.

Detailed listings of data for subjects experiencing NCI CTCAE grade 3 to 4 biochemistry and hematology values will be provided. All measurements collected, regardless of the number of days after the last dose of study drug, will be included in these listings.

Descriptive summary statistics for categorical ECG data will be presented for baseline and Day 1 of Cycle 1 and Cycle 3 (Arms 1 or 2 only). Visit window in [Table 2](#) will not be applied to the ECG data. Shift tables will also be provided.

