11.4.2 Assessment of Hepatotoxicity

The number and percentage of subjects with maximum treatment-emergent laboratory values meeting the following criteria were summarized to assess potential hepatotoxicity.

Potential hepatotoxicity criteria defined in Hy's law:

- $\text{ALT} \geq 3 \times \text{ULN}$ and $\text{total bilirubin} \geq 2 \times \text{ULN}$

- $AST \geq 3 \times ULN$ and total bilirubin $\geq 2 \times ULN$
- ALT and $AST \geq 3 \times ULN$ and total bilirubin $\geq 2 \times ULN$

The maximum ratio relative to the ULN will be used to determine if subjects met the criteria listed above. The ALT, AST, and total bilirubin values do not need to be concurrent in order to meet the defined criteria as long as collected up to 35 days following the last dose date of study drug (ABT-414/TMZ/lomustine). For ALT, AST, and total bilirubin, a subject will be counted if the post-baseline laboratory value up to 35 days following the last dose date of study drug (ABT-414/TMZ/lomustine) met the above criteria regardless of the baseline laboratory value (i.e., the post-baseline laboratory value does not need to be worse than the baseline laboratory value).

A listing of all ALT, AST, total bilirubin, and alkaline phosphatase values will be provided for all subjects who meet any of the criteria defined above.

11.5 Analysis of Vital Signs Using Criteria for Potentially Clinically Significant Vital Sign Values

Vital signs values will be assessed for potential clinical significance through the application of criteria developed by the sponsor as detailed in [Table 10](#).

Table 10. Criteria for Potentially Clinically Significant Vital Sign Values

Vital Signs Variables	Criterion	Definition of Potentially Clinically Significant Values
Systolic blood pressure	High	Value ≥ 160 mmHg
Diastolic blood pressure	High	Value ≥ 100 mmHg
Heart rate	Low	Value ≤ 50 bpm
	High	Value ≥ 120 bpm
Temperature	Low	Value $\leq 32^\circ\text{C}$
	High	Value $> 40^\circ\text{C}$

The number and percentage of subjects with post baseline values meeting Criteria for Potentially Clinically Significant Vital Signs values will be summarized. The baseline will be defined as the last non-missing measurement collected prior to or on the first dose

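### The laboratory safety baseline stops at randomization, so a pre-dose sample taken after it can count as post-baseline in the laboratory summaries that have no visit window

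*SAP*

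**What the plan says.** SAP 6.0 gives the general rule, subject to exceptions stated elsewhere: "the baseline observation is defined as the last non-missing measurement collected prior to or on randomization". It adds a fallback: "If no measurement collected prior to or on randomization, then the last non-missing observation prior to or on the first dose date".

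SAP 11.4 applies the same rule and fallback to laboratory toxicity grades. It takes as baseline this value: "grade of the last measurement collected prior to or on randomization, or if missing, then prior to or on the first dose". For changes from baseline in hematology, biochemistry and vital signs, 11.4 points back to the general rule: "vital sign parameters, changes from baseline are analyzed for each post-baseline visit (as specified in Section 6.0").

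SAP 11.5, which covers vital signs meeting criteria of potential clinical significance, uses a different anchor: "The baseline will be defined as the last non-missing measurement collected prior to or on the first dose". No reason is given for the difference.

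On timing, Protocol chapter 4 and SAP 4.2 say: "Treatment should start within 96 hours from randomization". Protocol 6.3.1 places day 1 evaluations within the three days before day 1 or on that day, before dosing.

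**The concern.** Any sample drawn after randomization and before the first dose is drug-free, and it is the measurement closest to the start of treatment. Under 6.0 and 11.4 it is not baseline if an earlier value exists. An earlier value will nearly always exist, because Protocol 6.2 requires hematology, biochemistry and vital signs within the two weeks before randomization. The fallback will therefore seldom apply.

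The SAP does not define post-baseline separately. If the word is read as anything after the baseline cut-off, a pre-dose abnormality can enter tables meant to describe what happened on treatment. The adverse-event tables, anchored to first dose, would treat the same abnormality differently. Vital signs would also carry two baselines in one safety report: one for mean change and another for the potentially clinically significant counts.

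**Working it through.** The documents state no figure that depends on the baseline rule, so there is nothing to reproduce. The check compares the rules and then traces where a gap sample goes.

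**1. The anchors side by side**

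| Analysis | Baseline anchor | Source |
|---|---|---|
| General rule | Randomization; first dose only as fallback | SAP 6.0 |
| Laboratory grade shifts | Same as 6.0 | SAP 11.4 |
| Vital-sign change from baseline | Refers to 6.0 | SAP 11.4 |
| Vital-sign potentially clinically significant counts | First dose | SAP 11.5 |
| Treatment-emergent adverse events | First dose | SAP 11.1 |

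**2. Can a sample fall in the gap?**

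The gap is at most 96 / 24 = 4 days. Protocol 6.3.1 lets screening results stand for cycle 1 day 1 if they were obtained within 14 days before day 1. Screening may precede randomization by 14 days, so its age at day 1 can reach 14 + 4 = 18 days. With a 4-day gap, reuse is allowed only if screening was at most 14 − 4 = 10 days before randomization. Screening done 11 to 14 days before must be repeated. The repeat window then runs from day 4 − 3 = 1 to day 4 after randomization, entirely inside the gap. The repeat is often optional, but not always.

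**3. Which Study Rx Day does a gap sample get?**

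Let first dose be *k* days after randomization and the sample *d* days after, with 0 < *d* ≤ *k*. Under SAP 6.0, Rx Day = *d* − *k* if *d* < *k*, and 1 if *d* = *k* (there is no Day 0).

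| *k* | Rx Days of samples after randomization, up to the first-dose day |
|---|---|
| 0 | None (a sample on the day of randomization is itself eligible as baseline) |
| 1 | 1 |
| 2 | −1, 1 |
| 3 | −2, −1, 1 |
| 4 | −3, −2, −1, 1 |

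The first post-baseline window in SAP Table 2 (Week 2) is Rx Days 2 to 18. No gap sample falls in it, so by-visit analyses use the sample neither as baseline nor as follow-up.

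**4. Which summaries have no window?**

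- *Maximum and final post-baseline grade (11.4).* The final grade has an upper limit of 35 days after last dose. No lower limit at first dose is stated for either grade. A gap sample could be the final value only if no later one exists.
- *Highest and lowest hematology values (11.4).* No bound at first dose is stated.
- *Potentially clinically significant laboratory values (11.4.1).* One qualifying post-baseline observation is enough.
- *Hepatotoxicity (11.4.2).* The opening sentence speaks of treatment-emergent values, but the counting rule then refers to post-baseline values up to 35 days after last dose. It disregards the baseline value and does not require the enzyme and bilirubin elevations to be concurrent.

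In each of these a drug-free value can be counted as the text stands.

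**5. Could the arms differ?**

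Protocol 5.2.1 recommends steroid eye drops starting 48 hours before ABT-414 dosing. If the drops begin only once the arm is known, the first ABT-414 infusion comes at least 2 days after randomization, while a control patient could start at once. In Arm 1, temozolomide could still be taken earlier. Gap samples may therefore be more common in the ABT-414 arms. This is an inference from the schedule; the documents do not say it.

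**The case against.** The strongest defence has four parts.

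- *The exception is permitted.* SAP 6.0 allows other rules where specified, its change list shows that the baseline definition was revisited, and a randomization anchor is defensible because the protocol times baseline assessments to randomization. This stands: 11.5 breaches nothing. A reader might infer that 11.5 proves the general rule to be an error, or that it governs all vital signs. The documents support neither reading, since it covers only the potentially clinically significant counts. What remains is an unexplained inconsistency.
- *Table 2 removes the samples.* This stands for by-visit analyses. A reader might infer that gap samples are counted as on-treatment throughout the safety report; the Rx Day windows rule that out. The windows do not reach the summaries listed in step 4.
- *Few results can change.* Entry limits in Protocol 3.2 are well short of the SAP thresholds: neutrophils at least 1.5 against below 1, platelets at least 100 against below 50 (all × 10⁹/L), AST below 2.5 against above 5 times the upper limit of normal. Such a test would have to worsen sharply within days, drug-free, to add a case. This largely stands, though lymphocytes and electrolytes have no entry limit. A patient already at grade 3 at screening does not create a shift from grades 0–2 to 3–4.
- *The tables are descriptive.* SAP 11.1 plans no comparisons, p-values or confidence intervals, and Protocol 8.2.3.7 says that whole-study safety tables do not account for baseline grades. A reader might infer that pre-treatment abnormalities will be formally attributed to the drug. The documents do not support that, because adverse events are anchored to first dose and laboratory tables assign no cause.

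**Conclusion.** The point holds in a limited form. The laboratory baseline is tied to randomization, the vital-sign criteria in 11.5 are tied to first dose, and the unwindowed laboratory summaries lack a lower bound at first dose. A drug-free sample taken after randomization can therefore be counted as post-baseline in those summaries. In the by-visit analyses, the value nearest to treatment start is lost.

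The documents do not say how many patients have a gap sample, so no count can be given. The number of altered table entries is probably small: the gap is at most four days, the day 1 repeat is often optional, and an entry changes only if the gap value is abnormal and no later value is as bad. Treatment-emergent adverse events and the efficacy endpoints do not depend on this.

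The conclusion assumes that post-baseline means after the baseline cut-off wherever no window is named; the SAP does not say otherwise. The correction is still worth making, because it needs no new data and makes the laboratory and adverse-event tables agree on when treatment starts.

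**What to change.** For laboratory and vital-sign safety analyses in SAP 6.0, 11.4 and 11.5, define baseline as the last non-missing value before the first dose of study drug, and post-baseline as after that first dose. Keep the randomization baseline for efficacy.

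Two clarifications would help. In Arm 1, first dose should mean the earlier of ABT-414 and temozolomide. Where no sampling time is recorded on the first-dose day, a protocol day 1 sample can be taken as pre-dose, because Protocol 6.3.1 schedules it before dosing.

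The cost is a sentence or two in the SAP and the matching change to the derivation programs, made before the SAP is signed off ahead of database lock. No extra data are needed.

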7.1 Demographic and Baseline Characteristics

Continuous demographic data (e.g., age, height, and weight) will be summarized with N, mean, standard deviation (St. Dev.), median, minimum, and maximum. Frequencies and percentages will be computed for the following parameters (but not limited to): sex, race, ethnicity, age group (< 40; 40 to < 60; ≥ 60 years old), weight, height, body mass index (BMI), WHO performance status, MGMT methylation status, EGFR vIII status, regions of the world, tobacco and alcohol use, timing of relapse (< 16 weeks; ≥ 16 weeks), chemotherapy (≤ 1; > 1), and surgery for glioblastoma recurrence (yes; no).

There will be no statistical comparison of demographic and baseline measurements between treatment arms.

7.2 Medical History

Medical history data will be summarized and presented using conditions/diagnoses as captured on the eCRF. The conditions/diagnoses will be presented in alphabetical order. The number and percentage of subjects with a particular condition/diagnosis will be summarized for each treatment arm. Subjects reporting more than one condition/diagnosis will be counted only once for that condition/diagnosis. There will be no statistical comparison of medical history between treatment arms.

